Study treatment will begin as soon as possible after signing the informed consent (as per section 5.2 of this protocol) and inclusion will be completed as per section 5.3 of this protocol.

The first administration of cabozantinib will be carried out after the infusion of the first atezolizumab cycle, the patient will take the treatment in the presence of a member of the Site staff who will advise the patient on the correct intake of the treatment (according to the indications of the section 7.1 of this protocol), discuss with the patient the process of completing the patient diary, and address the doubts that the patient may have at the time. In addition, patient must bring all medication bottle(s) (including empty ones) to each visit, for IMP adherence and compliance traceability purposes.

After the first supervised administration, cabozantinib will be self-administered by patients daily according to the indications of the Investigator staff and as indicated in section 7 of this protocol. Treatment with cabozantinib will be continuous until the progression of the disease and/or unacceptable toxicity, among others. Patients will attend follow-up visits with the study doctor every 3 weeks for clinical assessment, laboratory tests, laboratory determinations should be made within 72 hours prior to the date of administration of atezolizumab, in order to assess the relevance of administration of a new cycle (modifications, delays, etc.), according to what is specified in sections 7.1.2 and 7.2.2. Additionally, the study doctor may request patients to come to the centre more frequently in case of toxicity or discomfort of the patient. Additional information about the study's determinations is found in section 8 of this protocol.

Treatment and study determinations will be the same for all the patients, regardless of the cohort in which the patients are included.

This is a study with Simon's two-stage design; it requires that an event is observed in the first nine patients before continuing to the second stage where there is a possible inclusion of 15 additional patients (up to a maximum of 24 patients per cohort).

In addition, an optional biomarker study with tumour and blood samples will be performed (if it is feasible for the Sponsor), and it is detailed in the corresponding biological samples manual.

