7.1.2. Dose modifications

The allowed dosing schemes of this trial are:

- *Level 0 (starting dose): cabozantinib 40 mg qd + atezolizumab 1200 mg iv every 21 days (one cycle)*
- *Level -1: cabozantinib 20 mg qd + atezolizumab 1200 mg iv every 21 days (one cycle)*

If cabozantinib is temporarily or definitively interrupted for its toxicity, atezolizumab will be continued, unless the toxicity of cabozantinib prevents the administration of atezolizumab or increases the risk of atezolizumab toxicity. In this case, both treatments will be interrupted until toxicity resolution (or NCI CTCAE grade 1) or definitively.

If one of the two drugs is discontinued or interrupted due to toxicity, the administration of the other drug should continue according to the protocol schedule.

All dose reductions and interruptions (including any missed doses), and the reasons for the reductions/interruptions are to be recorded in the eCRF and patient record.

As previously mentioned, cabozantinib dose reduction to 20 mg qd is allowed. Once reduced, dose re-escalation of cabozantinib is allowed in the opinion of the Principal Investigator, taking into account clinical benefit, type and degree of toxicity that produced the dose reduction.

Cabozantinib should be withheld for:

- Intolerable Grade 2 adverse reactions
- Grade 3 or 4 adverse reactions
- Osteonecrosis of the jaw

Upon resolution/improvement (i.e., return to baseline or resolution to Grade 1) of an adverse reaction, reduce the dose as follows:

- If previously receiving 40 mg daily dose, resume treatment at 20 mg daily.
- If previously receiving 20 mg daily dose, resume at 20 mg if tolerated, otherwise, discontinue cabozantinib.

Permanently discontinue cabozantinib for any of the following:

- Severe hemorrhage
- Development of gastrointestinal (GI) perforation or unmanageable fistula
- Serious thromboembolic event (e.g., myocardial infarction, cerebral infarction)
- Hypertensive crisis or severe hypertension despite optimal medical management
- Nephrotic syndrome
- Reversible posterior leukoencephalopathy syndrome

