Diarrhoea, nausea/vomiting, decreased appetite, and stomatitis/oral pain were some of the most commonly reported GI adverse reactions. Prompt medical management, including supportive care with antiemetics, antidiarrheals, or antacids, should be instituted to prevent dehydration, electrolyte imbalances and weight loss. Dose interruption or reduction, or permanent discontinuation of cabozantinib should be considered in case of persistent or recurrent significant GI adverse reactions.

Diarrhea occurred in 63% of patients treated with cabozantinib. Grade 3 diarrhea occurred in 11% of patients treated with cabozantinib.

Withhold cabozantinib until improvement to Grade 1 and resume cabozantinib at a reduced dose for intolerable Grade 2 diarrhea, Grade 3 diarrhea that cannot be managed with standard anti diarrhea treatments, or Grade 4 diarrhea.

5) Thrombotic Events

Cabozantinib increased the risk of thrombotic events. Venous thromboembolism occurred in 7% (including 4% pulmonary embolism) and arterial thromboembolism occurred in 2% of cabozantinib-treated patients. Fatal thrombotic events occurred in cabozantinib-treated patients.

Discontinue cabozantinib in patients who develop an acute myocardial infarction or serious arterial or venous thromboembolic events that require medical intervention

6) Hemorrhage

Severe and fatal hemorrhages occurred with cabozantinib. The incidence of Grade 3 to 5 hemorrhagic events was 5% in cabozantinib-treated patients. Discontinue cabozantinib for Grade 3 or 4 hemorrhage. Do not administer cabozantinib to patients who have a recent history of hemorrhage, including hemoptysis, hematemesis, or melena.

7) Thrombocytopenia

In the HCC study (CELESTIAL), thrombocytopenia and decreased platelets were reported. Platelet levels should be monitored during cabozantinib treatment and the dose modified according to the severity of the thrombocytopenia (see section 7.1.2).

8) Wound Complications

Wound complications have been reported with cabozantinib. Stop cabozantinib at least 28 days prior to scheduled surgery. Resume cabozantinib after surgery based on clinical judgment of adequate wound healing. Withhold cabozantinib in patients with dehiscence or wound healing complications requiring medical intervention.

9) Hypertension and Hypertensive Crisis

Cabozantinib can cause hypertension, including hypertensive crisis. Hypertension was reported in 36% (17% Grade 3 and <1% Grade 4) of cabozantinib treated patients.

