Do not initiate cabozantinib in patients with uncontrolled hypertension. Monitor blood pressure regularly during cabozantinib treatment. Withhold cabozantinib for hypertension that is not adequately controlled with medical management; when controlled, resume cabozantinib at a reduced dose. Discontinue cabozantinib for severe hypertension that cannot be controlled with antihypertensive therapy or for hypertensive crisis.

10) Palmar-Plantar Erythrodysesthesia

Palmar-plantar erythrodysesthesia (PPE) occurred in 44% of patients treated with cabozantinib. Grade 3 PPE occurred in 13% of patients treated with cabozantinib.

Withhold cabozantinib until improvement to Grade 1 and resume cabozantinib at a reduced dose for intolerable Grade 2 PPE or Grade 3 PPE.

11) Proteinuria

Proteinuria was observed in 7% of patients receiving cabozantinib. Monitor urine protein regularly during cabozantinib treatment. Discontinue cabozantinib in patients who develop nephrotic syndrome.

12) Reversible Posterior Leukoencephalopathy Syndrome

Reversible Posterior Leukoencephalopathy Syndrome (RPLS), a syndrome of subcortical vasogenic edema diagnosed by characteristic finding on MRI, can occur with cabozantinib. Perform an evaluation for RPLS in any patient presenting with seizures, headache, visual disturbances, confusion or altered mental function. Discontinue cabozantinib in patients who develop RPLS.

13) Prolongation of QT interval

Cabozantinib should be used with caution in patients with a history of QT interval prolongation, patients who are taking antiarrhythmics, or patients with relevant pre-existing cardiac disease, bradycardia, or electrolyte disturbances. When using cabozantinib, periodic monitoring with on-treatment ECGs and electrolytes (serum calcium, potassium, and magnesium) should be considered.

14) Biochemical laboratory test abnormalities

Cabozantinib has been associated with an increased incidence of electrolyte abnormalities (including hypo- and hyperkalemia, hypomagnesaemia, hypocalcaemia, hyponatremia). It is recommended to monitor biochemical parameters during cabozantinib treatment and to institute appropriate replacement therapy according to standard clinical practice if required. Cases of hepatic encephalopathy in HCC patients can be

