attributed to the development of electrolyte disturbances. Dose interruption or reduction, or permanent discontinuation of cabozantinib should be considered in case of persistent or recurrent significant abnormalities (see section 7.1.2).

15) Osteonecrosis of the Jaw

Osteonecrosis of the jaw (ONJ) occurred in <1% of patients treated with cabozantinib. ONJ can manifest as jaw pain, osteomyelitis, osteitis, bone erosion, tooth or periodontal infection, toothache, gingival ulceration or erosion, persistent jaw pain or slow healing of the mouth or jaw after dental surgery. Perform an oral examination prior to initiation of cabozantinib and periodically during cabozantinib. Advise patients regarding good oral hygiene practices. Withhold cabozantinib for at least 28 days prior to scheduled dental surgery or invasive dental procedures, if possible. Withhold cabozantinib for development of ONJ until complete resolution.

16) Embryo-Fetal Toxicity

Based on data from animal studies and its mechanism of action, cabozantinib can cause fetal harm when administered to a pregnant woman. Cabozantinib administration to pregnant animals during organogenesis resulted in embryolethality at exposures below those occurring clinically at the recommended dose, and in increased incidences of skeletal variations in rats and visceral variations and malformations in rabbits.

Advise pregnant women of the potential risk to a fetus. Advise females of reproductive potential to use effective contraception during treatment with cabozantinib and for 4 months after the last dose.

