7.2.2. Atezolizumab dose modifications

There will be no dose reduction for atezolizumab in this study. Patients may temporarily suspend study treatment if they experience toxicity that is considered to be related to study drug and requires a dose to be held. If atezolizumab is held because of related adverse events for 42 days beyond when the dose would have been given, then the patient will be discontinued from atezolizumab and will be followed for safety and efficacy as specified in section 8. Please see Section 7.2.3 for guidelines for the management of infusion related reactions.

Dose interruption of atezolizumab

Any toxicity observed during the study treatment phase could be managed by interruption of the dose of the study treatment if deemed appropriate by the Investigator. Repeated dose interruptions are allowed as required, for a maximum of 42 days on each occasion. If the interruption is any longer than this, the Coordinating Investigator must be informed and treatment restart should be discussed between the Sponsor study team and the investigator. If in the judgment of the investigator, the patient is likely to derive clinical benefit from resuming atezolizumab after a hold of 42 days, the treatment may be restarted with the approval of the Coordinating Investigator.

If patients must be tapered off steroids used to treat adverse events, study treatment may be held for 42 days. The acceptable length of interruption will depend on agreement between the investigator and the Coordinating Investigator.

Study treatment must be interrupted until the patient recovers completely or the toxicity reverts to the National Cancer Institute Common Terminology Criteria for Adverse Events (NCI CTCAE version 5.0) grade 1 or less.

Treatment with atezolizumab must be temporarily or permanently interrupted if any NCI CTCAE grade 3 or 4 adverse event occurs which the Investigator considers to be related to the administration of atezolizumab. Dose interruptions for reason(s) other than toxicity, such as surgical procedures, may be allowed. The acceptable length of interruption will depend on agreement between the investigator and the Coordinating Investigator.

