7.3.1. Allowed concomitant treatment

- Antiemetics and antidiarrheal medications are allowed prophylactically according to standard clinical practice if clinically indicated.
- Granulocyte colony-stimulating factors (G-CSF or GM-CSF) are allowed if used per clinical guidelines (eg, ASCO or ESMO guidelines).
- Bisphosphonates can be used per standard of care if the benefit outweighs the risk per the Investigator's discretion.

Note: osteonecrosis of the jaw has been reported in subjects using bisphosphonates. Oral examinations are recommended at screening to determine eligibility and periodically during the study. In addition, subjects should be advised regarding oral hygiene practice and to quickly report symptoms to the Investigator. Frequent monitoring for potentially overlapping toxicities with study treatment is recommended.

- Transfusions and hormone replacement should be utilized as indicated by standard clinical practice.
- Inhaled, intranasal, intra-articular, or topical corticosteroids are allowed if minimal systemic absorption. Systemic corticosteroids are allowed for control of infusion reactions or irAEs and must be tapered over ≥ 1 month to a dose level ≤ 10 mg/day of prednisone equivalent before next atezolizumab administration. Prophylactic steroid treatment for subjects with contrast allergies prior to tumor imaging is allowed.
- Individualized anticoagulation therapy with heparin is allowed if it can be provided safely and effectively under the following circumstances:
 - Low dose LMWH for prophylactic use are allowed if clinically indicated and the benefit outweighs the risk per the investigator's discretion.
 - Therapeutic doses of LMWH after first dose of study treatment are allowed if clinically indicated (eg, for the treatment of DVT), and the benefit outweighs the risk per the investigator's discretion. For management of thromboembolic complications while on study, refer to Section 7.1.2 and 7.1.3
 - Accepted clinical guidelines regarding appropriate management while receiving anticoagulation therapy with heparins must be followed. This includes, but is not limited to, subject education regarding potential adverse drug reactions, monitoring laboratory parameters, dose adjustments (eg, due to kidney dysfunction, platelet decrease).
 - For restrictions on oral anticoagulants see Section 7.3.3.

Additional information on potential drug interactions with cabozantinib, atezolizumab are summarized in Section 7.4.1 and 7.4.2 respectively

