^b If corticosteroids have been initiated, they must be tapered over ≥ 1 month to the equivalent of ≤ 10 mg/day oral prednisone before atezolizumab can be resumed.

^c Resumption of atezolizumab may be considered in patients who are deriving benefit and have fully recovered from the immune-mediated event. The decision to rechallenge patients with atezolizumab should be based on investigator's assessment of benefit-risk and documented by both the investigator (or an appropriate delegate). Medical Monitor is available to advise as needed.

D) Management Guidelines for Endocrine Events

Event	Management
Asymptomatic hypothyroidism	
 Continue atezolizumab. Initiate treatment with thyroid replacement hormone. Monitor TSH closely.
Symptomatic hypothyroidism	
 Withhold atezolizumab. Initiate treatment with thyroid replacement hormone. Monitor TSH closely. Consider patient referral to endocrinologist. Resume atezolizumab when symptoms are controlled and thyroid function is improving.
Asymptomatic hyperthyroidism	
TSH ≥ 0.1 mU/L and < 0.5 mU/L:
 
 Continue atezolizumab. Monitor TSH every 4 weeks. Consider patient referral to endocrinologist. 
TSH < 0.1 mU/L:
 
 Follow guidelines for symptomatic hyperthyroidism. Consider patient referral to endocrinologist.
Symptomatic hyperthyroidism	
 Withhold atezolizumab. Initiate treatment with anti-thyroid drug such as methimazole or carbimazole as needed. Consider patient referral to endocrinologist. Resume atezolizumab when symptoms are controlled and thyroid function is improving. Permanently discontinue atezolizumab and contact Medical Monitor for life-threatening immune-mediated hyperthyroidism.

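### Cabozantinib restart after osteonecrosis of the jaw: Protocol 7.1.2 allows it at Grade 1, while 7.1.3 item 15 requires complete resolution

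*Combined protocol and SAP*

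**What the plan says.** Protocol 7.1.2 gives three grounds for withholding cabozantinib: intolerable Grade 2 reactions, Grade 3 or 4 reactions, and osteonecrosis of the jaw. The restart rule follows directly: "Upon resolution/improvement (i.e., return to baseline or resolution to Grade 1) of an adverse reaction, reduce the dose as follows". A patient on 40 mg resumes at 20 mg. A patient already on 20 mg resumes at 20 mg if that is tolerated, and otherwise stops. Osteonecrosis is not in the list of events that require permanent discontinuation, so it goes through this restart rule.

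Protocol 7.1.3 item 15, the warning specific to osteonecrosis, says: "Withhold cabozantinib for development of ONJ until complete resolution".

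Elsewhere 7.1.3 agrees with 7.1.2. For diarrhoea it says "Withhold cabozantinib until improvement to Grade 1 and resume cabozantinib at a reduced dose for intolerable Grade 2 diarrhea", and for palmar-plantar erythrodysesthesia "Withhold cabozantinib until improvement to Grade 1 and resume cabozantinib at a reduced dose for intolerable Grade 2 PPE or Grade 3 PPE".

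**The concern.** Two sections of one protocol set different thresholds for restarting the same drug after the same event. This is not simply a general rule beside a specific one, because 7.1.2 itself names osteonecrosis immediately before giving its restart condition. A site that follows 7.1.2 as written could resume cabozantinib while the jaw lesion is still present at Grade 1, which the warning in 7.1.3 forbids. Another site that follows 7.1.3 would wait. What is at stake is dosing safety and consistency between sites. No efficacy conclusion depends on it.

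**Working it through.** The plan states no figure for this point, so the main check is a comparison of the texts.

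**Step 1. Apply both rules to each state of a held patient with no osteonecrosis at baseline.**

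| State of the osteonecrosis | 7.1.2 | 7.1.3 item 15 | Agree? |
|---|---|---|---|
| Above Grade 1 | hold | hold | yes |
| Grade 1, not resolved | restart allowed | hold | no |
| Completely resolved (back to baseline) | restart allowed | restart allowed | yes |

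For such a patient, return to baseline is the same as complete resolution. The conflict therefore lies in the Grade 1 branch alone.

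**Step 2. Is the stricter wording likely to be deliberate?** In 7.1.3 the diarrhoea and erythrodysesthesia items use improvement to Grade 1, as 7.1.2 does. The osteonecrosis item departs from that pattern, which suggests an intended exception that 7.1.2 does not carry.

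**Step 3. Does any text settle precedence?** None was found. Items 1, 7 and 14 of 7.1.3 refer back to 7.1.2, but 7.1.2 has no pointer forward to 7.1.3. For thromboembolic events, 7.3.1 does name both: "For management of thromboembolic complications while on study, refer to Section 7.1.2 and 7.1.3". No equivalent exists for restart after osteonecrosis.

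**Step 4. How many patients?** Inputs:
- Rate of osteonecrosis: under 1% of patients treated with cabozantinib (7.1.3 item 15), taken here as an upper bound of 0.01.
- Patients: minimum 54 = 6 cohorts × 9; maximum 144 = 6 cohorts × 24 (synopsis and 10.1). The maximum requires all six cohorts to pass the first stage.

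Expected cases = rate × patients:
- 0.01 × 54 = 0.54
- 0.01 × 144 = 1.44

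Chance of at least one case = 1 − (1 − rate)^n:
- 1 − 0.99^54 = 0.419
- 1 − 0.99^144 = 0.765

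If the true rate were 0.1% (an assumption), the chances would be 1 − 0.999^54 = 0.053 and 1 − 0.999^144 = 0.134.

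All of these count osteonecrosis of any kind. Only cases that reach Grade 1 without resolving meet the conflict, and the documents do not give that share.

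**The case against.** The best defence is that 7.1.3 item 15 is the specific safety instruction, directly follows 7.1.2, and can be obeyed without breaching 7.1.2, since waiting for complete resolution satisfies both. A careful site that reads all of section 7 would probably choose it. That is fair, and it keeps the point minor. It does not remove the contradiction, because 7.1.2 also names osteonecrosis and no text gives 7.1.3 priority.

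Three stronger readings are tempting, and the documents do not support them.

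- *That 5.1 sends sites to 7.1.2 alone.* Section 5.1 does refer to "administration of a new cycle (modifications, delays, etc.), according to what is specified in sections 7.1.2 and 7.2.2". That sentence, however, concerns laboratory tests before each atezolizumab infusion. The same section sends cabozantinib intake, and treatment modifications and delays, to section 7 as a whole, which includes 7.1.3.
- *That the atezolizumab restart rules conflict in the same way for thyroid events.* Section 7.2.2 says "Study treatment must be interrupted until the patient recovers completely or the toxicity reverts to the National Cancer Institute" criteria's Grade 1 or less, while Appendix 1 D says "Resume atezolizumab when symptoms are controlled and thyroid function is improving". But 7.2.3 item 4 directs endocrine events to Appendix 1, so the appendix probably governs. The two rules would differ only for a patient still above Grade 1 once symptoms are controlled. The documents do not reproduce the thyroid grade criteria needed to show that any patient falls there.
- *That the conflict has up to a 76.5% chance of arising.* That figure bounds the chance of at least one osteonecrosis of any kind, at the maximum enrolment and the top of the stated rate. It is not the chance of an unresolved Grade 1 case.

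**Conclusion.** The inconsistency is real and minor. It is confined to a patient whose osteonecrosis is at Grade 1 but unresolved: 7.1.2 permits restart and 7.1.3 item 15 does not. At most a very few patients would be affected: fewer than 0.54 expected cases of any osteonecrosis in 54 patients or 1.44 in 144, with an unknown smaller number in the gap. This assumes that the protocol's stated rate of under 1% carries over to this combination and population. The only possible harm is a restart earlier than the warning allows. The response-rate decision in each cohort, the sample size and the error rates do not change. No finding is made on atezolizumab restart after thyroid events.

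**What to change.** In Protocol 7.1.2, after the restart list, add: *For osteonecrosis of the jaw, withhold cabozantinib until complete resolution; then resume at 20 mg daily if tolerated, otherwise discontinue.* This wording covers patients held from either 40 mg or 20 mg, since the protocol has no level below 20 mg.

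The cost is one sentence in the next amendment and a short letter to sites. Design, visits, sample size and analysis stay as they are.
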